Sample size and power calculations for this study are based on the hypothesis that the precision evaluation arm is superior to the usual care arm on the time-to-first event of the composite 3-component endpoint: all-cause death, non-fatal MI, or invasive cardiac catheterization without obstructive CAD (obstructive CAD defined as diameter stenosis $\geq 50\%$, FFR ≤ 0.80 , or iFR ≤ 0.89) over a 12-month of follow-up. Time to event analysis will use the date of the event, including the date of catheterization at which the absence of obstructive CAD is demonstrated. Assuming 10% of usual care participants will receive angiography as a first test results in an 8% primary endpoint event rate at 1 year in the usual care group and 5% event rate in the precision care group (i.e., 3% absolute [37.5% relative] effect size). Assumptions used in the primary endpoint event rate calculations (i.e., 8% vs. 5%) were: overall 10% will not receive randomized evaluation, and within the precision evaluation arm, approximately 20% will be assigned to guideline-recommended care with symptom management and no planned testing, of whom about 30% will have escalation of care to cCTA with selective FFRCT.

Randomizing 1050 participants per group (2100 total participants) is estimated to provide at least 90% power to detect a relative risk reduction of 37.5% in the precision evaluation arm (see Table 1 below, or refer to the power curves in the protocol). Sample size/power calculations are based on the log-rank test with 12-month accrual period, a minimum 12-month follow-up (i.e. last participant will be followed for at least 12-months), 10% attrition rate (i.e. lost to follow-up, dropouts) and a two-sided type I error rate of 0.05.

The DSMB will review interim analysis data for efficacy as well as possible sample size re-estimation. At any interim analyses, the O'Brien-Fleming boundary generated by Lan-DeMets alpha-spending function will be utilized as a statistical stopping rule (See DSMB charter for more details).

Table 1. The total number of participants needed for 85%, 90%, and 95% power. Although this is not an event-driven study, the table below also provides total number of MACE needed.

1-year event rate in precision evaluation arm	Power	Total number of Primary Events needed	Total number of participants needed
(37.5% ^{2%} effect size)	85%	173	1792
	90%	202	2096
	95%	250	2592

8. Database Sources

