The primary and major secondary endpoint comparisons between the randomized groups in this study will be performed according to the principle of intention-to-treat; that is, participants will be analyzed according to the treatment (evaluation) arm to which they were randomized, regardless of subsequent crossover or post-randomization strategy.

The log-rank a non-parametric test will be the primary statistical methodology to test for outcome differences between precision care arm and usual care arm with respect to the primary composite endpoint. The Cox proportional hazards model will be used to estimate the average treatment effect size using the hazard ratio (HR) and 95% confidence interval (CI) with treatment assignment as the only covariate in the model. The proportionality assumption (constant hazard over time) in the Cox model will be assessed using the cumulative sums of martingale residuals and the Kolmogorov-type Supremum test. Although log-rank statistic (primary method) is robust under non-proportional hazards it's not optimal due to loss of some statistical power. Thus, if the proportional hazards assumption is violated a two-stage procedure will be implemented (Qiu and Sheng 2008). Due to interim analysis conducted by the DSMB, the final analysis type I error rate (α) will be adjusted as $0.05 - \alpha$ spent at any interim analyses. Cumulative event rates will be calculated according to the method of Kaplan-Meier for each randomized arm as a function of time (in days) from randomization to the time of event or censoring + 1, and the estimated event probabilities will be displayed graphically.

As a supportive analysis, adjusted HRs and 95% CIs will be estimated using the Cox proportional hazards model by including pre-specified baseline risk factors as covariates in the model. These covariates will include: age, sex, CAD equivalent (diabetes, history of peripheral artery disease, or cerebrovascular), and intended first test strata: invasive/non-invasive.

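### Used as the significance level of the final log-rank test, 0.05 minus alpha spent is stricter than the Lan-DeMets O'Brien-Fleming boundary and leaves overall type I error below 5%.

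*SAP*

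**What the plan says.** SAP Section 7 (Sample Size and Power Calculations) sizes the trial with a log-rank test at "a two-sided type I error rate of 0.05". It says the DSMB will review interim data for efficacy and possible sample size re-estimation, and that at any interim the O'Brien-Fleming "boundary generated by Lan-DeMets alpha-spending function will be utilized as a statistical stopping rule". For this rule it adds "See DSMB charter for more details".

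SAP 9.2 (Primary Efficacy Analysis) then deals with the final test: "Due to interim analysis conducted by the DSMB, the final analysis type I error rate" "will be adjusted as $0.05 - \alpha$ spent at any interim analyses".

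Neither section gives a critical value for the final look, the number or timing of interim looks, or an information fraction. Neither says whether the quantity in 9.2 is a p-value threshold or an amount of error still to be spent. The final protocol (VIII.A and VIII.B) gives the overall two-sided 0.05 but no rule for the final look. SAP Section 3 says that the SAP supersedes the protocol on analysis plans, so the sentence in 9.2 is the only rule the analyst has for judging the final primary p-value.

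**The concern.** A type I error rate for the final analysis, marked as α, is most naturally taken as the level against which the final p-value is compared. Subtracting the alpha already spent and testing at the remainder is a Bonferroni-type split: it treats the chance of rejecting at the interim and the chance of rejecting at the end as if they simply added. They overlap, because the final log-rank statistic contains the interim data. A spending function takes account of this overlap and so permits a higher nominal level at the last look.

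At stake is the pass/fail line for the one confirmatory primary test. A final p-value between the two levels would be negative under the literal wording of 9.2 and positive under the boundary family named in Section 7. That dispute would arise after unblinding. Some power would also be given up, in a trial whose 2100 participants are only 4 more than the 2096 that a fixed-sample calculation at 0.05 requires for 90% power.

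**Working it through.** **The plan's own figure.** Inputs from SAP Section 7: "an 8% primary endpoint event rate at 1 year in the usual care group and 5% event rate in the precision care group"; 12-month accrual; 12-month minimum follow-up; 10% attrition; two-sided 0.05. SAP Section 6 gives 1:1 allocation.

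- Hazard ratio under exponential survival: ln 0.95 / ln 0.92 = 0.615.
- Freedman events for 90% power: [(1 + 0.615)/(1 − 0.615)]² × (1.960 + 1.282)² ≈ 185 (unrounded hazard ratio).
- Mean event probability with uniform accrual and exponential loss of 10% per year: 0.0884.
- N = 185.09 / 0.08837 ≈ 2095.

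The same steps give 1790 and 2590 for 85% and 95% power. The SAP table has 1792, 2096 and 2592, so the sample size reproduces. It is a fixed-sample calculation at 0.05, with no allowance for interim looks.

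**The two final levels.** Assume one interim look at information fraction t. The looks are not given in the documents, so t is varied from 33% to 90%.

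1. Alpha spent at the interim, O'Brien-Fleming-type function with 0.025 per side: s(t) = 4[1 − Φ(2.241/√t)], where 2.241 is the upper 0.0125 normal point. At t = 0.50: 2.241/0.707 = 3.170, so s = 0.0031.
2. Interim critical value c₁: the two-sided normal point for s(t). At t = 0.50, c₁ = 2.963.
3. Lan-DeMets final critical value c₂: solve P(|Z₁| < c₁ and |Z₂| < c₂) = 0.95, with Z₁ and Z₂ standard bivariate normal and correlation √t. At t = 0.50, c₂ = 1.969, a nominal level of 0.0490.
4. Subtraction: nominal level 0.05 − s(t). At t = 0.50 this is 0.0469, critical value 1.987.
5. Overall alpha under subtraction: 1 − P(|Z₁| < c₁ and |Z₂| < subtraction value), with the same correlation.
6. Power: the same probabilities with drift 1.960 + 1.282 = 3.242, which gives 90% in a fixed-sample test. This matches the plan's "at least 90% power to detect a relative risk reduction of 37.5% in the precision evaluation arm".

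| Interim information | Alpha spent | Lan-DeMets final level (z) | Subtraction level (z) | Overall alpha under subtraction | Power, Lan-DeMets vs subtraction | Loss (points) |
|---|---|---|---|---|---|---|
| 33% | 0.0002 | 0.0499 (1.961) | 0.0498 (1.962) | 0.050 | 89.99% vs 89.97% | 0.0 |
| 50% | 0.0031 | 0.0490 (1.969) | 0.0469 (1.987) | 0.048 | 89.9% vs 89.6% | 0.3 |
| 67% | 0.0121 | 0.0463 (1.993) | 0.0379 (2.076) | 0.042 | 89.7% vs 88.2% | 1.5 |
| 75% | 0.0193 | 0.0442 (2.012) | 0.0307 (2.161) | 0.038 | 89.5% vs 86.9% | 2.6 |
| 90% | 0.0363 | 0.0401 (2.053) | 0.0137 (2.465) | 0.037 | 89.4% vs 85.1% | 4.3 |

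Losses are taken from unrounded powers.

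**Sensitivity.** Earlier extra looks change little, because cumulative spend depends on the last interim. With looks at 50% and 75%, the final levels are 0.0440 and 0.0307 and overall alpha is 0.0386. Entering 0.05 directly in the spending function gives the same pattern: overall alpha 0.0467 for a look at 50% and 0.0378 at 75%.

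**The other reading.** If 0.05 − s(t) is the error still available for the final look, the final critical value is the c₂ of step 3 and overall alpha is exactly 0.05.

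**The case against.** The strongest reply is that 9.2 states an identity of alpha spending: the error left for the last look is total alpha minus cumulative spend. On that reading 9.2 and Section 7 agree, and nothing in 9.2 mentions a p-value threshold. This stands in part. A reader might infer that 9.2 contradicts the Lan-DeMets design, and the wording does not establish that. It does admit two thresholds, and the more natural one departs from the design.

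A reader might also infer that a final test stricter than 5% is itself the fault. It is not: every Lan-DeMets final level in the table is below 0.05 too. The fair comparison is with that boundary.

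The direction is conservative. No reading inflates type I error, and the estimate and analysis population are unaffected. For an early look the two rules practically coincide. All of that stands and limits the weight of the point.

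The DSMB charter may hold the looks and even a final critical value. It is not among the documents, so the size cannot be fixed. However, Section 7 cites the charter for the interim stopping rule, and nothing there displaces the sentence in 9.2 on the final test.

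**Conclusion.** The point holds as an ambiguity whose natural reading is conservative. Applied literally as the final significance level, the rule in SAP 9.2 is stricter than the final boundary of the design in Section 7, and overall two-sided error falls below the stated 0.05. For one look between 50% and 90% information, overall alpha is about 0.037 to 0.048 and the cost is about 0.3 to 4.3 power points from a 90% fixed-sample design.

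This rests on an assumed look time, O'Brien-Fleming-type spending at 0.025 per side, and the usual joint normality of successive log-rank statistics. The documents support neither a claim of inflated error nor a single figure for the loss.

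**What to change.** Replace the sentence in SAP 9.2 with:

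> The final primary-endpoint p-value will be compared with the nominal two-sided level given by the Lan-DeMets O'Brien-Fleming spending function at the actual information fractions, so that cumulative two-sided type I error is 0.05.

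This corrects the literal reading and makes the other one explicit. State the planned number and timing of looks beside it. The cost is one SAP sentence, with no new data, best made before unblinding.

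The sentence covers a standard group-sequential log-rank test. If sample size is re-estimated (Section 7), or the two-stage procedure for non-proportional hazards is used (9.2), error control needs its own statement.

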9.3 Secondary Endpoint Analyses

9.3.1 Finkelstein-Schoenfeld/Win Ratio Test

The key secondary analysis of PRECISE will use the Finkelstein-Schoenfeld method (Finkelstein and Schoenfeld 1999) as modified by Pocock (“win ratio”, calculated without matching). The main objective of the FS/win ratio test is to calculate the treatment comparison test statistic based on relative clinical importance of the components in the primary composite endpoint rather than relying on the time-to-first occurrence approach. For this analysis the win-ratio (95% CI) will be estimated using the three components of the primary endpoint as tie breakers: 1) all-cause death, 2) non-fatal MI, and 3) invasive cardiac catheterization without obstructive CAD. In general terms, each pair of participants assigned to either precision care or usual care arm will be placed into one of the hierarchical groups as follows (with comparison through the shortest follow-up achieved for each member of the pair):

1. Shortest time to occurrence of death; if neither died or there is a tie then move to #2
2. Shortest time to occurrence of first non-fatal MI; if neither had non-fatal MI or there is a tie then move to #3
3. Shortest time to occurrence of first invasive cardiac catheterization without obstructive CAD; if neither had invasive cardiac catheterization without obstructive CAD or there is a tie then move to #4
4. None of the above (a tie is declared)

Handling of Dropouts and Missing Data: All participants with follow-up are expected to have some data to address this endpoint. The win-ratio (WR) approach of (Pocock et al., 2012) will be used to evaluate each composite endpoint as well as the calculations of the WR test statistic p-values. In the unmatched WR approach, all possible pairing between participants in the

precision arm and participants in the usual care arm will be considered. Then, each pair will be classified into one of the categories (1-4) listed above. The 95% CI for the estimated WR will be calculated using a bootstrap approach (Davison and Hinkley, 1997) and the method described in Luo et al., 2015. Multiple imputation method will be used to account for missing follow-up data (Little RJ et al., 2012). Similarly, multiple imputation method will be used to impute missing baseline values.

9.3.1 Analysis of Economic Endpoints

Economic analyses are intended as descriptive analyses with estimates of treatment differences and precision of those estimates as the principal results of analysis. Statistical tests, when performed, will serve a subsidiary role in assisting interpretation. No adjustment for multiplicity is planned. For the economic outcomes, the primary comparisons will be at 6 months between treatment arms by intention-to-treat. Additional comparisons will examine 45-day and 12-month outcomes. Details of these analyses are contained in a separate PRECISE Economics and QoL SAP.

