Endpoints will be assessed at 45 days, 6 months, and 1 year. Secondary endpoints include:

1. Hierarchical analysis (Finkelstein and Schoenfeld (FS) and Pocock's win ratio) of primary endpoint (gives priority to clinical importance of the components of the composite outcome rather than time to event)
2. Resource use patterns (all participants) and medical costs (US participants): resources to be assessed include index testing, follow up testing, diagnostic and other cardiac procedures and hospitalizations. Primary comparisons will be made at 12 months.
3. QoL: the Seattle Angina Questionnaire (SAQ) will be used to assess angina-specific Quality of Life; the EuroQol 5D (EQ-5D-5L) survey will be used for a brief assessment of overall (generic) health status; patient satisfaction with diagnostic process will be assessed once at 45 days using a 4-item instrument created for this trial.
4. Death: All-cause, cardiovascular, non-cardiovascular
5. Myocardial infarction: All, procedural, spontaneous MI
6. Hospitalizations: All, cardiovascular, non-cardiovascular, and for progressive or unstable angina
7. Rates of preventive medication use (ASA, statins) in participants with clinical indication for use: hyperlipidemia, diabetes, documented CAD
8. Cumulative radiation exposure at 1 year
9. Proportion of invasive coronary angiogram patients who undergo revascularization (PCI or CABG) within 6 months of enrollment (catheterization efficiency)

IV.D. Rationale for the Selection of Outcome Measures

Rationale for Clinical Assessments

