unlikely (by definition) to have significant obstructive CAD. The managing clinician is encouraged to treat them with guideline-recommended preventive care, anti-anginal medications and other medical therapy as deemed appropriate to their clinical circumstances. This is expected to control or eliminate symptoms in most participants. In the unlikely event that symptoms are intractable or accelerating, despite reasonable medical treatment or if other compelling reasons for additional evaluation are present, testing may be warranted.

Unless there are urgent or emergent indications to proceed with invasive testing, all such participants requiring testing should have a cCTA followed by selective FFR_{CT} rather than stress testing or elective invasive catheterization. cCTA with selective FFR_{CT} should only be pursued if the participant is having:

1. Unstable/accelerating symptoms (i.e. no longer falls into stable angina cohort)
2. Continued stable symptoms despite risk factor modification including:
 - a) Optimized blood pressure control with goal <130/80 mmHg
 - b) Optimized lipid management with high-intensity statin in appropriate patients
 - c) Optimized diabetes management with blood glucose control in appropriate patients
 - d) Antiplatelet therapy in appropriate patients
 - e) Tobacco cessation in patients who smoke
 - f) Lifestyle counseling regarding diet exercise and stress reduction
 - g) Anti-anginal therapy including utilization of beta-blockers, calcium channel blockers, short and long-acting nitrates, and/or ranolazine

The assignment to no immediate testing is not time limited and is valid for the duration of the participant's enrollment in the trial. Testing in such participants should be infrequent and the reasons for this will be carefully documented and monitored.

V.F. Participant Withdrawal

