For the Economics outcomes, primary comparison will be at 12 months between treatment arms by intention-to-treat. All-cause hospitalizations, cardiovascular hospitalizations, ER visits not resulting in hospitalization, and major outpatient procedures will be enumerated. In addition, we will examine length of stay by intensity of care, numbers of CTAs, noninvasive stress tests (stress perfusion imaging, stress echocardiography, exercise electrocardiography, stress cardiac magnetic resonance imaging), invasive tests (invasive coronary angiography, invasive fractional flow reserve or equivalent, optical coherence tomography, intravascular ultrasound), coronary revascularization procedures (coronary artery bypass graft surgery (CABG), percutaneous coronary intervention (PCI), number of coronary stents), and cardiac medications (beta blockers, aspirin, statins, antiplatelet medications).

Confidence intervals for differences will be estimated using the bootstrap approach. Differences in resource use will be interpreted in the context of the trial clinical results, looking for both consistency and plausibility. Descriptive comparisons of intensity of care/resource consumption according to clinical variables defining subgroups of interest will be performed. The primary economic analyses will focus on the US enrollment and in secondary analyses, resource use patterns for all patients enrolled in the trial will be compared by intention-to-treat to develop an understanding of the degree to which treatment related differences in the trial are region dependent.

Analyses of Medical Costs

To compare medical costs between treatment arms, we must: 1) assign costs to all medical resources consumed during the study period; 2) compute mean costs by treatment group (defined by the principle of intention-to-treat); and 3) calculate the difference in mean costs between treatment arms and generate confidence intervals.

A) Derivation of Cost Estimates

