Primary statistical comparisons of costs between the two treatment groups will be performed using the intention-to-treat principle. A nonparametric partitioned estimator will be used to estimate diagnostic strategy-specific, 1-year medical costs with 4 partitions corresponding to follow-up intervals following randomization. Comparisons between the two testing strategies will be made using a normal approximation with standard errors estimated using the bootstrap approach. Bootstrapping will be performed using 10,000 repetitions, with percentile-based confidence intervals reported. The primary cost comparison will be made for cumulative costs at 12 months. The primary effect size will be the mean cost difference between the two arms with 95% confidence intervals. P values will be calculated for selective comparisons, with a “significant” p value equivalent to a 95% confidence interval that excludes 0. No adjustment in significance levels for multiple comparisons will be used.

Differences in cost will be interpreted in the context of the trial clinical results, looking for both consistency and plausibility. Costs will be presented both overall and by category (e.g., inpatient hospitalization, outpatient procedures, concomitant medications, non-acute institutional care). Hospitalizations will be classified as cardiovascular or non-cardiovascular by the Clinical Events Committee. For illustrative purposes, we will use bootstrap methods to plot the probability of a difference in total costs greater than arbitrary thresholds of interest (such as \$500, \$750, or \$1000).

C) Cost Sensitivity Analyses

In secondary sensitivity analyses, we will compare resource use and costs between treatment groups in the US. In this manner, the effect of overall patterns of resource use in the US cohort versus ex-US on cost differences by treatment group can be assessed. We will also perform a per protocol analysis of costs.

Analyses of Quality of Life Outcomes

For each of the QOL measures examined in this study, we will provide simple descriptive and comparative analyses by intention-to-treat. To address the multiple comparisons problem arising from testing each individual scale and time point separately, we propose two complementary approaches. First, we will pre-specify the angina frequency scale from the SAQ as the primary QOL comparison of interest and assign all other comparisons to a secondary (supportive) status.

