Figure 4.12.3.1	Mean observed and predicted mean Prognostic Value of Risk Score for Lowest risk: No CAD + No Event All Randomized Participants, Only Precision Care Arm Receiving CTA
Table 4.12.3.2	Mean observed and predicted mean Prognostic Value of Risk Score for Lowest risk: No CAD + No Event All Randomized Participants, Only Precision Care Arm Receiving CTA
Figure 4.12.4.1	Mean observed and predicted mean Prognostic Value of Risk Score for Significant or Severe CAD All Randomized Participants, Only Precision Care Arm Receiving CTA
Table 4.12.4.2	Mean observed and predicted mean Prognostic Value of Risk Score for Significant or Severe CAD All Randomized Participants, Only Precision Care Arm Receiving CTA
Table 4.13.1	Comparisons of outcomes in low PRMS and elevated risk Adjudicated Endpoint Collection and Summary All Randomized Participants, Low PRMS Only
Figure 4.13.1.1	Kaplan-Meier Plot of Primary Endpoint All Randomized Participants, Low PRMS Only
Figure 4.13.1.2	Kaplan-Meier Plot of Primary Endpoint Component All Cause Death All Randomized Participants, Low PRMS Only
Figure 4.13.1.3	Cumulative incidence Plot of Primary Endpoint Component 1st Non-fatal MI All Randomized Participants, Low PRMS Only
Figure 4.13.1.4	Cumulative incidence Plot of Primary Endpoint Component 1st Invasive cardiac catheterization without obstructive CAD All Randomized Participants, Low PRMS Only
Table 4.13.2	Comparisons of outcomes in low PRMS and elevated risk Adjudicated Endpoint Collection and Summary All Randomized Participants, Elevated PRMS+athero Only
Figure 4.13.2.1	Kaplan-Meier Plot of Primary Endpoint All Randomized Participants, Elevated PRMS+athero Only
Figure 4.13.2.2	Kaplan-Meier Plot of Primary Endpoint Component All Cause Death All Randomized Participants, Elevated PRMS+athero Only
Figure 4.13.2.3	Kaplan-Meier Plot of Primary Endpoint Component 1st Non-fatal MI All Randomized Participants, Elevated PRMS+athero Only
Figure 4.13.2.4	Kaplan-Meier Plot of Primary Endpoint Component 1st Invasive cardiac catheterization without obstructive CAD All Randomized Participants, Elevated PRMS+athero Only
Table 4.15.1	COVID-19 Sensitivity Analysis of Primary Endpoint Endpoint Collection and Summary All Randomized Participants

11. Changes from the Protocol

The current version of the protocol is v1.5, dated 15- OCT-2019. Under section VIII.B., the time to event is defined as the date of the first event minus the date of randomization, and we are adding 1 to this value.

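### The SAP makes 6 months the primary economic time point where the final protocol says 12 months, and does not declare the change

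*SAP*

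**What the plan says.** **Final protocol, v1.5.** Three statements agree on 12 months.

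- IV.C, secondary endpoint 2 (resource use and costs): "Primary comparisons will be made at 12 months".
- VIII.B, Analysis of Resource Use Endpoints: "For the Economics outcomes, primary comparison will be at 12 months between treatment arms by intention-to-treat".
- VIII.B, Cost Comparisons: "The primary cost comparison will be made for cumulative costs at 12 months". The estimator described there is for 1-year costs in four partitions. Section VI.B collects resource use through 1 year.

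**SAP.** The section headed Analysis of Economic Endpoints (the second of two sections numbered 9.3.1) says: "For the economic outcomes, the primary comparisons will be at 6 months between treatment arms by intention-to-treat". It continues: "Additional comparisons will examine 45-day and 12-month outcomes". It also describes the role of these analyses: "Economic analyses are intended as descriptive analyses with estimates of treatment differences", with tests subsidiary and no multiplicity adjustment. Details are left to a separate Economics and QoL SAP, which is not among the documents.

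**Precedence and declared changes.** SAP section 3 says that the SAP overrides the protocol on endpoints and analyses. SAP section 11 names protocol v1.5 as current and lists one change only: "the time to event is defined as the date of the first event minus the date of randomization, and we are adding 1 to this".

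**The concern.** Costs are part of the primary objective in both documents, and protocol II.A states an expectation of net savings with the precision strategy. The time point called primary determines which estimate carries that conclusion. Here the governing document halves the horizon that the protocol states three times. Neither the change nor a reason for it is recorded in the section meant for that purpose.

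The horizon matters in this design because some testing is deferred. Protocol V.E says of low-risk precision participants: "The assignment to no immediate testing is not time limited and is valid for the duration of the participant's enrollment in the trial". A longer window is better able to separate testing that was avoided from testing that was only postponed. Late costs can arise in usual care as well, and a 6-month comparison omits those too.

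There is a related ambiguity. SAP 4.1.1 places resource use and costs among the secondary endpoints assessed by the Benjamini-Hochberg procedure, while the economic section plans no multiplicity adjustment. If costs do enter that family, the choice of primary time point presumably decides which comparison enters.

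**Working it through.** **1. The texts side by side**

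| Item | Final protocol v1.5 | SAP |
|---|---|---|
| Primary economic time point | 12 months (IV.C; VIII.B twice) | 6 months |
| Status of 12 months | Primary | Additional |
| Status of 6 months | Follow-up contact | Primary |
| Change declared in SAP section 11 | – | No; only the +1 day convention |

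All of these are current texts, so none of the difference comes from the amendment log. The documents give no economic sample size, expected cost difference or standard deviation, so there is no planned figure to reproduce.

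**2. Size of the deferred-testing pathway**

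Inputs from SAP section 7: 1050 participants per arm; about 20% of the precision arm assigned to no planned testing; about 30% of those escalating to cCTA.

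- Assigned to no planned testing: 1050 × 0.20 = 210.
- Expected to escalate: 210 × 0.30 = 63, which is 63/1050 = 6% of the arm.
- Expected never to be tested: 210 − 63 = 147, which is 14% of the arm. The testing avoided in this group does not depend on the horizon.

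**3. Share falling after month 6**

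Let f be the share of the 63 escalations that occur after month 6. The documents do not give f, so the whole range is shown. The number left out of a 6-month comparison is 63 × f.

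| f (assumed) | cCTAs after month 6 | Share of precision arm |
|---|---|---|
| 0 | 0 | 0% |
| 0.25 | 15.75, about 16 | 1.5% |
| 0.50 | 31.5, about 32 | 3.0% |
| 0.75 | 47.25, about 47 | 4.5% |
| 1 | 63 | 6.0% |

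One reference case assumes a constant escalation hazard that reaches 30% at 12 months:

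- Escalated by month 6: 1 − √0.70 = 0.163.
- Escalated after month 6: 0.300 − 0.163 = 0.137.
- f = 0.137/0.300 = 0.456, and 63 × 0.456 = 28.7, about 29 participants (2.7% of the arm).

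**4. From tests to a cost difference**

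This step cannot be done. It needs unit costs, the timing of escalation, and late testing and procedure costs in both arms, and the documents give none of these. At equal unit cost, late additional testing in the same share of usual-care participants (somewhere in 0-6%, matching f) would cancel the imbalance from the deferred tests.

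**The case against.** The strongest case on the other side accepts the mismatch in the texts and disputes its consequence. A reader might infer that the shorter horizon tilts the cost result toward the precision arm, because usual-care testing is done early and precision testing is deferred. The documents do not support that inference, for four reasons.

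- The schedule places the initial test before the 45-day visit in both arms. About 80% of the precision arm is assigned to cCTA at the outset, so those costs also fall inside 6 months.
- Usual care has late costs too. SAP section 6 bars cCTA and calcium scoring only for the first 45 days, and later testing and procedures are at the clinicians' discretion. The plan also assumes more primary events over the year in usual care (8% against 5%). A 6-month cut could therefore understate a saving.
- Escalation need not be late. Protocol V.E lists unstable or accelerating symptoms as a criterion separate from persistent symptoms despite medical measures, and it expects such testing to be infrequent.
- Late costs are not lost. They are collected, and the SAP still compares the arms at 12 months, so a saving that was only postponement could show there.

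All four points stand. Two further arguments carry less weight. The Economics and QoL SAP may explain the choice, but this SAP states the 6-month rule itself and omits it from its own list of changes. Protocol IV.D argues that later outcomes are less directly tied to the evaluation strategy, which could be used to defend a shorter horizon. There, however, it justifies 12 months against longer follow-up.

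Nor does the descriptive label settle the matter. The SAP makes the estimates the principal economic results, so which one is primary still counts.

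**Conclusion.** Wrong as written. The SAP contradicts the final protocol's primary economic time point and does not declare that it does so. This rests on the texts alone and needs no assumption.

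The consequence is limited. Late costs in both arms move from the headline estimate to an additional comparison. For deferred cCTA in the precision arm this concerns 0 to 63 of 1050 participants (0-6%), and about 29 under the assumed constant hazard. Those counts rest on the plan's 20% and 30% assumptions and are not a cost bias. Direction and size of any effect on the cost difference are unknown, so neither a bias in favor of the precision arm nor a loss of the 12-month result should be claimed. The point is a document error to correct before the economic analysis. It does not touch the primary clinical endpoint.

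**What to change.** In the SAP section on economic endpoints, make 12 months the primary comparison for resource use and cumulative cost, with 45 days and 6 months as additional comparisons. Make the Economics and QoL SAP agree. In the same edit, state whether costs belong to the Benjamini-Hochberg family of SAP 4.1.1 and, if so, at which time point.

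Twelve months includes late costs in both arms whichever way they fall. It also fits the 1-year estimator already in the protocol.

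If the sponsor keeps 6 months, section 11 should declare the change, give the reason, and date the decision relative to data access. Both horizons should then be reported side by side, and any cost-saving conclusion should rest on the 12-month estimate.

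The cost is one sentence in this SAP and a matching check of the Economics SAP. No new data are needed, since resource use is collected through 1 year. The downside is that the 12-month estimate may be less precise than the 6-month one.
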